4.3 Derived variables

Source data	Derivation rule	Label	Format
Date of last use of study product, date of D0 visit	TRT_DUR_D=Date of last use of study product – date of D0 visit +1	Treatment duration in days	Numeric
Date of end of study, date of selection visit	STUDY_DUR_D=Date of end of study – date of selection visit +1	Study duration in days	Numeric
OSDI total score	IF 0<=OSDI total score < 13 THEN OSDI_CL_D=1 IF 13<= OSDI total score < 23 THEN OSDI_CL_D=2 IF 23<= OSDI total score < 33 THEN OSDI_CL_D=3 IF 33<= OSDI total score < 100 THEN OSDI_CL_D=4	OSDI score in class	1 = "OSDI none" 2 = "OSDI Mild" 3 = "OSDI moderate" 4 = "OSDI severe"
Total Oxford score of the examined eye (i.e. worse eye defined at D0) at day 0, Total Oxford score of the corresponding eye at day 35 (i.e. day 84)	EVOL_OX_D0D35 (i.e. D84) = Total Oxford score of the examined eye (i.e. worse eye defined at D0) at day 35 (i.e. day 84) - Total Oxford score of the corresponding eye at day 0	Change of the Oxford total score from baseline to day 35 (i.e. day 84)	Numeric
Same derivation rule as above for changes on OSDI total score, Van Bijsterveld total score, Schirmer test result, TBUT total score, all ocular dryness symptoms score from D0 to D35 and from D0 to D84.			

Total Oxford score of the examined eye (i.e. worse eye defined at D0) at day 0, Total Oxford score of the corresponding eye at day 35 (i.e. day 84)	EVOL_OXREL_D0D35 (i.e. D84) = (Total Oxford score of the examined eye (i.e. worse eye defined at D0) at day 35 (i.e. day 84) - Total Oxford score of the corresponding eye at day 0) / Total Oxford score of the corresponding eye at day 0	Relative change of the Oxford total score from baseline to day 35 (i.e. day 84) in percentage	Numeric
Same derivation rule as above for changes (relative variation) on OSDI total score, Van Bijsterveld total score, Schirmer test result, TBUT total score, all ocular dryness symptoms score from D0 to D35 and from D0 to D84.			
Adverse Event	IF at least one adverse event is reported for the patient, ALO_AE=1 ELSE, ALO_AE=0	At least one AE	0 = "No" 1 = "Yes"
Same derivation rule as above for at least one TEAE, at least one severe AE, at least one AE related to the treatment, at least one SAE, at least one AE that lead to study withdrawal			

5 SEQUENCE OF PLANNED ANALYSES

5.1 Interim analyses

No interim analysis is planned.

5.2 Final analyses and reporting

All final planned analyses identified in the protocol and in this SAP, will be performed only after the last patient has completed assessments scheduled for the study period and the database has been cleaned and locked. A blinded data review will be conducted by members of the Trial Management Committee (TMC) prior to locking and archiving the trial database. Treatment allocations will not be un-blinded and no un-blinded analyses will begin until this SAP has been reviewed by the TMC.

5.3 Changes to statistical information in the clinical trial protocol

Not applicable.

6 STATISTICAL METHODOLOGY

6.1 Detailed power and sample size

The primary objective of this study is to confirm the non-inferiority of DM05 in comparison with Optive® reference for global ocular staining assessed with a 0-15 score (Oxford score). The clinical non-inferiority margin was set at 2 points on the Oxford score. Assessing a standard-deviation equal to 2.5, a total of 68 patients (34 patients in each group) was required to reach a power of 90% to set-up the non-inferiority based on a bilateral confidence interval at 95%. Assuming a drop-out rate of 15%, 80 patients will be randomized in the study to keep sufficient power for main analysis of the primary endpoint (analysis on PP population).

6.2 Generalities for statistical analyses

Continuous variables will be summarized by number of non-missing observations, mean, standard deviation, minimum, median, maximum.

Categorical data will be summarized by frequency and percentage of patients in each category. Percentages will be based on non-missing observations.

All statistical tests will be 2-tailed with a Type I error of 0.05 unless otherwise stated.

6.3 Multiple Imputations for Handling of Dropouts or Missing data

In the case of missing values on the primary endpoint, a sensitivity analysis with the last observation carried forward (LOCF) method will be applied using at each visit the last observation available for analysis on ITT and PP population.

6.4 Adjustments for Covariates

Subject characteristics collected at the selection visit will be described globally and by treatment group on the PP and the ITT population:

- Sex
- Age
- Total Oxford score of worse eye at D0

If some differences on Age and/or Sex between treatment groups on PP population at inclusion were to be significant, a sensitivity analysis of the primary endpoint will be added. The model considered will be the same as the primary analysis model, including Age and/or Sex as covariate.

If the number of patients included in the ITT population but excluded from the PP population is sufficient, the variables above will also be compared between patients included in the PP population and those excluded from the PP population (among ITT population), to confirm the homogeneity of both sub-populations regarding these outcomes.

6.5 Multiple Comparisons/Multiplicity

Not applicable

7 STATISTICAL ANALYSES

After the database lock and the randomisation code release, the statistical analysis will be performed by the statistician of Axonal-Biostatem, using SAS® software, according to the Statistical Analysis Plan (SAP) approved by the Validation Committee.

7.1 Study Populations

7.1.1 Protocol Deviations

Definition of minor and major deviations will be provided. Number of subjects with at least one major/minor deviations will be computed.

A listing of all the protocol deviations observed during the Data Review will be provided, and protocol deviations will be summarized in tables, for the whole population.

7.1.2 Analysis Populations

Number of patients in each population will be described globally and by treatment group thanks to a flow-chart.

Three population will be defined:

- Intention to treat (ITT) population corresponding to all patients randomized.
- Safety population corresponding to all patient randomized and having received at least one dose of treatment
- Per Protocol (PP) population corresponding to patients of the safety population who will not present major protocol deviation.

Protocol deviations will be defined by the Data Review Committee during a blind review process day.

The main analysis of the main criterion will be conducted on the PP population.

The same analysis will be performed on ITT population (with and then without imputation of missing data – see section 7.6.1, paragraph sensitivity analysis).

In case of conclusion of non-inferiority of DM05 compared to Optive®, a superiority analysis will be performed on the ITT population and then on the PP population.

Secondary criteria will be performed on ITT population and PP population.

[figure not shown]
Safety analysis will be performed on the Safety population

7.2 Patient accountability

Will be described:

- Number of included and randomized patients
- Number of randomized patients by treatment groups
- Number of active centre
- Number of included and randomized patients by treatment groups
- Number of included and randomized patients by centre
- Number of patients at each visit.
- Number and percentage of patients having finished the study normally by treatment groups.
- Reason of withdrawal will also be tabulated and a listing of reason of withdrawal will be produced.
- First and last visit date of first patient included as well as first and last visit date of last patient included
- Treatment duration in days will also be described by treatment group. It will be derived according to the formula below:
Date of last use of study product – date of D0 visit +1
- Study duration in days will also be described by treatment group. It will be derived according to the formula below:
Date of end of study – date of selection visit +1
- Normal study end (yes/no) and if no, reason

Patients accountability will be described thanks to the flowchart below:

7.3 Demographic and Baseline Characteristics

Parameters below will be described globally and by treatment group on PP population. They will then be compared between patients included in the PP population and those included in ITT population:

- Demographic data
 - o Sex
 - o Age
- Corneal fluorescent staining (Oxford scale) at D0 visit
 - o Total score of worse eye

Parameters below will be described globally and by treatment groups on the ITT population:

- Demographic data
 - o Sex
 - o Age
- Contraception (for female only)
 - o Childbearing potential (yes/no)
 - o If no, reason
 - o If yes, contraceptive method (yes/no)
 - o If yes type of contraceptive method

A listing of other contraceptive method will be added if applicable
- Medical history at selection visit
 - o At least one ophthalmological history among the last 12 months (yes/no)
 - o A listing of ophthalmological history will then be produced including event start and end date and event preventing inclusion (yes/no)
 - o At least one medical or surgical event among the last 12 months (yes/no) and any allergic history (yes/no)
 - o A listing of medical, surgical and allergy history will then be produced
- Product and document dispensation
 - o Dispensation of artificial tears without preservative (NaCl 0.9%): Hydrabak®
 - o Number of vials dispensed
- Ocular surface disease index (OSDI) at both selection visit and D0 visit
 - o Subtotal A, B and C of OSDI score
 - o Total OSDI score
- Corneal fluorescent staining (Oxford scale) at both selection visit and D0 visit
 - o Subtotal score right, middle and left of right eye
 - o Total score of right eye
 - o Subtotal score right, middle and left of left eye
 - o Total score of left eye
- Tear film Break Up Time (TBUT) at both selection visit and D0 visit
 - o Measurement 1, 2 and 3 for both right and left eye
 - o Total score for both right and left eye
- Schirmer test at both selection visit and D0 visit
 - o Length of paper wetting in mm for both right and left eye
 - o Total score for both right and left eye

- Pregnancy test (women with childbearing potential only – D0 visit)
 - o Realisation of urinary pregnancy test (yes/no)
 - o If no, reason
 - o If yes, result of the test
- Definition of the worse eye (D0 visit)
 - o Worse eye defined

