9.1 Planned tables

Subjects with at least one major/minor deviations

Protocol deviations

Analysis populations

Number of active centre

Number of included and randomized patients

Number of included and randomized patients by treatment groups

Number of included and randomized patients by centre

Course of the study

Number of patients having finished the study normally by treatment groups.

Reason of withdrawal

Study follow-up

Normal study end

Demographic data by treatment groups – PP population

Demographic data by PP/ITT population

Contraception (for female only) by treatment groups – PP population

Contraception (for female only) by PP/ITT population

Medical history at selection visit by treatment groups – PP population

Medical history at selection visit by PP/ITT population

Product and document dispensation by treatment groups – PP population

Product and document dispensation by PP/ITT population

Ocular surface disease index (OSDI) at selection visit by treatment groups – PP population

Ocular surface disease index (OSDI) at selection visit by PP/ITT population

Ocular surface disease index (OSDI) at D0 visit by treatment groups – PP population

Ocular surface disease index (OSDI) at D0 visit by PP/ITT population

Corneal fluorescent staining (Oxford scale) at selection visit by treatment groups – PP population

Corneal fluorescent staining (Oxford scale) at selection visit by PP/ITT population

Corneal fluorescent staining (Oxford scale) at D0 visit by treatment groups – PP population

Corneal fluorescent staining (Oxford scale) at D0 visit by PP/ITT population

Tear film Break Up Time (TBUT) at selection visit by treatment groups – PP population

Tear film Break Up Time (TBUT) at selection visit by PP/ITT population

Tear film Break Up Time (TBUT) at D0 visit by treatment groups – PP population

Tear film Break Up Time (TBUT) at D0 visit by PP/ITT population

Schirmer test at selection visit by treatment groups – PP population

Schirmer test at selection visit by PP/ITT population

Schirmer test at D0 visit by treatment groups – PP population

Schirmer test at D0 visit by PP/ITT population

Pregnancy test (women with childbearing potential only – D0 visit) by treatment groups – PP population

Pregnancy test (women with childbearing potential only – D0 visit) by PP/ITT population

Definition of the worse eye (D0 visit) by treatment groups – PP population

Definition of the worse eye (D0 visit) by PP/ITT population

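### SAP 7.3 and SAP 6.4 give conflicting instructions for the same baseline check: PP against ITT, which overlap, or PP against the patients excluded from PP

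*SAP*

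**What the plan says.** SAP 7.1.2 defines the two sets. The first is "Intention to treat (ITT) population corresponding to all patients randomized". The second is "Per Protocol (PP) population corresponding to patients of the safety population who will not present major protocol deviation". The safety population is itself made up of randomized patients, so PP is nested in ITT.

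SAP 7.3 lists sex, age and the D0 Oxford total score of the worse eye, to be described on PP. It then adds: "They will then be compared between patients included in the PP population and those included in ITT population". No test is named. For the remaining baseline variables 7.3 plans only a description on ITT.

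SAP 6.4 lists the same three variables and asks that they be "compared between patients included in the PP population and those excluded from the PP population", within ITT. This is conditional: "If the number of patients included in the ITT population but excluded from the PP population is sufficient". The stated aim is "to confirm the homogeneity of both sub-populations regarding these outcomes".

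SAP 9.1 lists fourteen baseline tables split by PP/ITT, for example "Demographic data by PP/ITT population". None is titled as PP against excluded patients.

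**The concern.** The main non-inferiority analysis is run on PP, so a reader will want to know whether the patients removed from PP differ from those kept. That is the purpose given in 6.4. A comparison of PP with all of ITT cannot serve it, because most of the patients on the two sides are the same people and any real difference is diluted.

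A programmer also has two instructions for one check. The 7.3 version is unconditional and resembles the 9.1 titles. The 6.4 version depends on an undefined number and has no table of its own. If the 7.3 version is the one produced, the output will look reassuring almost regardless of who was excluded.

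**Working it through.** **Planned sizes.** SAP 6.1 gives margin 2, SD 2.5, two-sided 95% interval, power 90%, 34 per arm (68 in all), 15% drop-out and 80 randomized.

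- Normal formula: n per arm = 2 × (1.960 + 1.282)² × 2.5² / 2² = 32.8, so 33.
- Noncentral t: power 0.893 at 33 per arm and 0.902 at 34, so 34 per arm reproduces.
- 68 / (1 − 0.15) = 80 reproduces.

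**Assumed split.** The number who will be excluded from PP is not in the documents. I take 80 − 68 = 12 as the central case, which treats planned drop-out as exclusion from PP, and use 4 to 20 as the range.

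**Dilution.** With N patients in ITT and e of them excluded from PP:

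mean(ITT) − mean(PP) = (e/N) × [mean(excluded) − mean(PP)].

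This is exact, and it holds for proportions (sex) as well as means. At e = 12 the factor is 12/80 = 0.15. As an illustration only, a 2-point gap in D0 Oxford score would appear as 0.15 × 2 = 0.3.

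**If an independent two-sample test were applied to PP and ITT.** In SD units with p = N − e = 68:

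- Standard error the test would use: √(1/68 + 1/80) = 0.1649.
- True standard error of the difference: 0.15 × √(1/68 + 1/12) = 0.0470.
- Ratio: 0.0470 / 0.1649 = 0.285. The nominal 1.96 cut-off therefore acts as 1.96 / 0.285 ≈ 6.9 true standard errors, and the type I error is about 6 × 10⁻¹² instead of 0.05.

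Power at a true gap of 1 SD between excluded and PP patients (normal formula, two-sided 5%):

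| Excluded of 80 | Share of gap shown | 2-point gap appears as | PP vs ITT | PP vs excluded |
|---|---|---|---|---|
| 4 | 5% | 0.1 | 0.000 | 0.50 |
| 8 | 10% | 0.2 | 0.000 | 0.77 |
| 12 | 15% | 0.3 | 0.0001 | 0.89 |
| 16 | 20% | 0.4 | 0.011 | 0.95 |
| 20 | 25% | 0.5 | 0.095 | 0.97 |

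A simulation of t-tests (40,000 runs, 68 and 12 patients) agrees. With no gap, PP vs ITT rejected in none of the runs and PP vs excluded in 5.1%. At 1 SD the rates were 0.000025 and 0.88. At 1.5 SD they were 0.0013 and 0.997. The normal formula gives 0.018 for PP vs ITT at 1.5 SD; the t-test rejects less often because its pooled SD grows with the gap.

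The near-zero power does not extend to extreme gaps: at 2 SD the formula gives 0.31 for PP vs ITT with 12 excluded, and 0.99 with 20.

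**Tables.** Of the fourteen PP/ITT titles in 9.1, two cover the variables that 7.3 compares: demographic data and Oxford at D0. The other twelve concern contraception, medical history, dispensation, OSDI (two visits), Oxford at selection, TBUT (two), Schirmer (two), pregnancy test and worse eye.

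**The case against.** A reader might infer that the SAP prescribes an invalid significance test and that the plan hides differences between included and excluded patients. The documents support neither.

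- **The valid contrast is already planned.** SAP 6.4 specifies PP against excluded patients for the same three variables, so the plan as a whole does not conceal the difference. This stands, with the limit that 6.4 is conditional on an undefined number.
- **No test is named in 7.3.** An independent two-sample test is only an inference, supported indirectly by the p-value column in the generic templates of SAP 8.4. Showing PP and ITT side by side descriptively is legitimate. This stands, but the dilution applies to a descriptive display too, so it still cannot show selection.
- **The fourteen titles do not all follow 7.3.** Only two match its variables, a PP/ITT title does not say how the columns are formed, and SAP 9 calls the list informational and open to change. This stands.
- **The split and the 2-point gap are assumptions.** The inclusion criterion for a qualifying eye is an Oxford score of 4 to 9, so a 2-point difference in means is 40% of that 5-point window: an illustration, not an expected effect.
- **No decision hangs on this check.** The primary analysis is repeated on ITT and deviations are tabulated, so selection into PP is also examined elsewhere. This stands and keeps the point small.

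**Conclusion.** The point holds as an internal inconsistency. SAP 7.3 and 6.4 define different contrasts for one baseline check, and the 7.3 contrast cannot serve the purpose stated in 6.4. It shows only e/N of any real gap: 15% at an assumed 12 of 80 excluded, 5% to 25% for 4 to 20. If an independent two-sample test were run on it, power at a 1 SD gap would be between 0 and 0.09 over that range, against 0.50 to 0.97 for PP versus excluded. The dilution is exact arithmetic; the power figures depend on the assumed test, split and gap. This is a minor correction to a supportive check. The primary non-inferiority analysis, its alpha and its sample size do not change.

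**What to change.** 1. In SAP 7.3, replace the comparison of PP with ITT by PP versus ITT patients not in PP, as in 6.4. Make the same change in the two 9.1 titles concerned (demographic data; Oxford at D0).
2. Show this contrast at least descriptively whatever the number excluded, so that it no longer depends on an undefined threshold. If a test is kept, name it. With few patients excluded even the right test is weak (0.50 at 1 SD with 4 excluded), so a non-significant p-value alone should not be read as confirming homogeneity.
3. Reconcile the other twelve PP/ITT titles in 9.1 with 7.3, which plans only an ITT description for those variables.

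A display of excluded patients by arm is optional; at the assumed split it would cover about 6 patients per arm (12/2).

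The cost is SAP wording and table titles, with no new data and no effect on the primary analysis.

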7.4 Previous and concomitant medication

Will be described, on the ITT population only:

- o Did the subject take/stop/modify any medical treatment within the last 6 months at each visit (yes/no)
- o An individual data listing of all current or past medication treatment will be produced including centre number / patient id / treatment group / inclusion date (D0) / end of study date / age / sex / drug name / indication / dosage / administration route / specification / treatment start date / treatment end date / duration / treatment relationship / treatment preventing inclusion or leading to exclusion

7.5 Follow-up analyses

Will be described at each follow-up visit, by treatment group, on the ITT population only:

- Product and document dispensation (D35 and D84)
 - o Average posology
 - o Posology precision
 - o Frequency of use
 - o Frequency precision
- Pregnancy test (women with childbearing potential only –D84)
 - o Realisation of urinary pregnancy test (yes/no)
 - o If no, reason
 - o If yes, result of the test

7.6 Efficacy analyses

7.6.1 Primary Efficacy Endpoint

Primary endpoint derivation

The primary efficacy endpoint is the difference of the change from baseline to day 35 of the Oxford total score in the worse eye between the two patient groups (DM05- Optive®).

The Oxford scale range to 0 (normal) to 15 (greater cornea and conjunctiva staining). An improving of Oxford scale is expected.

The change of the Oxford total score from baseline to day 35 will be derived as below:

Total Oxford score of the examined eye (i.e. worse eye defined at D0) at day 35 - Total Oxford score of the corresponding eye at day 0.

Descriptive analyses:

- Right, middle and left Oxford sub-scores as well as total score will be described on the worse eye at D0 and D35 by treatment groups on both ITT and PP population.
- Change from D0 to D35 of the Oxford total score on the worse eye will be described by treatment groups on both ITT and PP population.

Non-inferiority analysis (main analysis)

In order to demonstrate the non-inferiority of DM05 compared to Optive®, the difference of this change will then be tested between groups in the PP population (DM05 minus Optive®): A two-way analysis of covariance (ANCOVA) model will be constructed using main effects of treatment and baseline score as covariate Adjusted means (least square mean and error standard of the mean) by treatment will be presented as well as an estimate of the difference between adjusted means.

A 95% two-sided confidence interval, based on the ANCOVA model, will be computed for the difference of DM05 minus Optive®:

- If the upper bound of the CI is no higher than 2 points, then the null hypothesis (DM05 is inferior to Optive®) will be rejected.
- Else, if the upper bound is greater than 2, the non-inferiority is not demonstrated.

The result will be presented as follow:

Population	DM05	Optive	Difference DM05 - Optive	95% CI	P non inferiority	P superiority***
Day 0 (baseline) mean (SD)	X1	Y1				
Day 35 mean (SD)	X2	Y2				
Adjusted change between Day 0 and Day 35 - LSM (SEM)	[X2-X1]*	[Y2-Y1]*	[X2-X1] -[Y2- Y1]	[Min - Max**]		

* These values were expected as negative, meaning an improvement of the Oxford score.

** The upper bound indicates the maximal difference of change in disfavor of DM05.

*** In case of demonstration of non- inferiority.

[figure not shown]

Figure 1: interpretation of results —Estimate of the difference and 95% CI are presented for 4 situations.

The p value of non-inferiority will be expressed taking on board the predefined margin of non-inferiority.

The MIXED procedure (SAS®) will be used.

SAS code:

```
proc mixed data=XX order=data;
  where PP = 1 ;
  class TT;
  model EVOL = BASELINE TT /* Other covariates can be added here */;
  lsmeans TT / diff;
run;
```

In case of conclusion of non-inferiority of DM05 compared to Optive®, the superiority of DM05 compared to Optive® will then be tested on both ITT and PP population in the same way as described above for the non-inferiority:

- If the upper bound of the CI is no higher than 0 points, then the null hypothesis (DM05 is not superior to Optive®) will be rejected. meaning that DM05 is superior to Optive.
- Else, if the upper bound is greater than 0, the superiority is not demonstrated.

Sensitivity analysis

1. If a statistically difference will appear between the 2 groups at baseline on age and/or sex, a sensitivity analysis will be conducted on PP population with the same used for main analysis including this or these factor(s).

The same analysis will be performed on ITT population with imputation of values in case of missing data with LOCF technique (baseline value or value in case of withdrawal).

The result will be presented in the same way as the main analysis.

2. Centre + treatment + interaction treatment*centre will be tested on the primary end point. If p value is lower than 0.10, it is declared that there is an interaction between treatment and centre. In this situation, a sensitivity analysis will be conducted on PP population with the same factors used for main analysis including this factor.

The same analysis will be performed on ITT population with imputation of values in case of missing data with LOCF technique (baseline value or value in case of withdrawal)

